Study Procedures and Assessments	Study Visits: 
▪ Enrollment/Baseline Visit▪ Device Implant Visit▪ 7-day Post-Procedure Follow-up Visit▪ 1-month Follow-up Visit▪ 2-month Follow-up Visit▪ 3-month Follow-up Visit▪ 6-month Follow-up Visit▪ 12-month Follow-up Visit▪ 24-month Follow-up Visit 
Enrollment/Baseline Visit: The study-specific informed consent form must be signed prior to any study-related activities, at which time a subject will be considered enrolled in the study. Each subject must meet all inclusion and no exclusion criteria to be eligible to participate in the study. At the baseline visit, data will be gathered from subjects including relevant medical history and recent OAB medications. The MESA Urinary Incontinence Questionnaire will be used to exclude predominant stress incontinence. Subjects are prohibited from additional OAB treatment until after the 12-month follow-up visit, starting two weeks prior to the baseline voiding diary and completion of the baseline Overactive Bladder Quality of Life (OAB-q) questionnaire. A negative pregnancy test is required for women of childbearing potential.
 
The urinary voiding diary will be explained and given to the subject to be completed for 3 consecutive days. The Overactive Bladder Quality of Life Questionnaire (OAB-q), [REDACTED] [REDACTED] and Urgency Perception Scale (UPS) questionnaires, will be collected.
 
Between consent and prior to the neurostimulator placement, an ultrasound image to assess measurements related to the tibial nerve may be completed in a subset of patients to summarize the subject's anatomical characteristics.
 
Any adverse events reported following informed consent will be collected.

----------------------------------	---

Device Implant Visit:

It is recommended that the device is implanted within 30 days of the subject's enrollment in the study. The device will be implanted in accordance with the Medtronic TNM Clinician Guide. Motor and sensory thresholds will be assessed during the procedure.

During this visit, the device will be interrogated, sensory/motor thresholds assessed, the amplitude will be set, and the subject will be discharged with a compression sock. An ultrasound of the tibial nerve may be completed following the neurostimulator implant procedure.

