9.3 Inclusion Criteria

To be eligible to participate in the study, a subject must meet all the following inclusion criteria:

1. Subjects 18 years of age or older
2. A 3-day voiding diary demonstrating a minimum of 3 episodes of urinary urge incontinence in 72 hours
3. Have a diagnosis of UUI for at least 6 months

4. No OAB pharmacotherapy for 2 weeks prior to completion of the baseline voiding diary and Overactive Bladder Quality of Life (OAB-q) questionnaire
5. Failed, or are not a candidate for, conservative non-pharmacologic treatment (e.g., pelvic floor training, biofeedback, behavioral modification)
6. Failed and/or are intolerant* to at least 2 overactive bladder medications (antimuscarinics or beta-3 agonist) or contraindicated to all pharmacological therapies for the treatment of overactive bladder
7. Willing and able to accurately complete study diaries, questionnaires, attend visits, operate the system, and comply with the study protocol
8. Willing and able to provide signed and dated informed consent

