- Any changes to the stimulation should be made within the first five minutes of each therapy session.
- It is recommended that the device is recharged weekly.

Any adverse events and/or device deficiencies will be collected.

6-Month Follow-up Visit:

The 3-day urinary voiding diary should be started approximately one week prior to the study visit. If the diary is not able to be completed prior to the visit, it will be completed immediately following the study visit. The Overactive Bladder Quality of Life Questionnaire (OAB-q), [REDACTED]

Scale (UPS) [REDACTED] will be collected.

Urgency Perception

The subject will have an impedance check and sensory/motor threshold testing done with their foot in the same relaxed position as the time of implant. The subject's sensory and motor threshold will be identified using 20 hertz, 200 microseconds pulse width stimulation and titrating up amplitude until the sensory threshold, highest acceptable amplitude and motor threshold are confirmed. The neurostimulator amplitude should be set to the highest acceptable amplitude. If highest acceptable amplitude is unable to be found, it is recommended to set the amplitude to two times the motor or sensory threshold, whichever is lower. The comfort of the programmed amplitude will be verified while the subject is in expected positions and adjusted for comfort, if needed.

If the sensory threshold, highest acceptable amplitude and/or motor threshold are not observed, this will be documented. The Investigator or delegated personnel should try repeating the motor and sensory assessment with the foot in a different position. If the motor and/or sensory response is still not observed, the Investigator or delegated personnel should set neurostimulator amplitude to 3 mA unless an alternative amplitude level is recommended by the Sponsor.

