14.1.5 Diary Data Analysis

The primary and several other objectives and additional measures are based on the analysis of voiding diary data. The diary will be collected for 3 days prior to or after each study visit. The site will assign each diary to the corresponding visit in the eCRF. In some cases, the diary might be completed for slightly less or more than 3 days (e.g., for 68 or 75 rather than the expected 72 hours). All diaries which are greater than 48 hours will be used for analysis. For UI, UUI, and UF, the total number of episodes will be determined for each subject's diary collection period at each visit. The actual total length of the diary for each visit will be determined by using the subject-specific diary start and end time reported by the site. The number of episodes will be divided by the total length of the diary for that subject at the visit and reported as a daily (24 hour) rate (i.e., 'per day'). The change will be determined by subtracting the baseline value per day from the follow-up value per day. Percentage change will be determined by dividing the change in episodes per day by the baseline value. Negative values for change and percentage change represent an improvement. Responder rate for UUI is defined as the proportion of TNM subjects experiencing a reduction of 50% or more in daily urinary urge incontinence (UUI) episodes. Responder rate for UF is defined as the proportion of TNM subjects experiencing a reduction of 50% or more in daily urinary frequency (UF) episodes or a return of voiding to <8 voids per day. Responder rate for UI is defined as the proportion of TNM subjects experiencing a reduction of 50% or more in daily urinary incontinence (UI) episodes. Responder rate for urinary urgency (UU) is defined as the proportion of TNM subjects with an improvement of at least 1 point on the UPS. OAB responder rate is defined as the proportion of TNM subjects who are considered either a UUI, UF, or UU responder.

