Additional supporting analyses to further understand the primary objective will be completed through analyses of the change in UUI (secondary objective) and percentage change in UUI (additional measure).

To assess the robustness of the primary objective results under the influence of missing data, sensitivity and subgroup analyses will be conducted using alternative missing data methods and by including different subsets of subjects. The first sensitivity analysis will be completed including subjects from the Primary Objective Complete Case analysis set. This analysis set will be used for a second sensitivity analysis which will be completed including only subjects who received stimulation ('As treated analysis') at the 6-month follow-up visit. An analysis will also be completed to evaluate UUI responder rate differences between different programs. A tipping point sensitivity analysis will also be completed. A final sensitivity analysis will be conducted on the Primary Objective Complete Case analysis set assigning response failure for all subjects who took OAB medication or received an advanced therapy from implant to the 6-month follow-up visit.

Complete Case analysis set subgroup analyses will be done for the following subject groups: sex, age (divided by median age; divided by age 65), race, and ethnicity. Subjects on the demographic cut point will be added to the adjacent group containing fewer subjects. Any subgroup with less than 10 subjects will not be reported.

As an exploratory analysis to assess if treatment effect differs by study center, a supporting analysis will be completed, as described in 14.1.4. This analysis will test whether the treatment effect is homogeneous between study centers for the UUI responder rate at 6 months.

UUI responder rate will be assessed over time through 24 months as part of the additional measures.

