## 7.9 Evaluation of Objectives

### 7.9.1 Primary Objective

#### 7.9.1.1 Primary Objective – UUI Responder Rate

To demonstrate that the percentage of subjects who are considered a UUI responder after 6 months of tibial neuromodulation exceeds a performance goal of 40%.

**Hypothesis:** The percentage of subjects who are considered a UUI responder 6 months after tibial neuromodulation implantation is greater than 40%.

$$H_0: p \leq 40\%$$

$$H_A: p > 40\%$$

Where  $p$  = the percentage of subjects who are UUI responders

**Endpoint Definition and Derivation:** A 3-day urinary voiding diary will be used to collect bladder symptoms, including UUI episodes. The primary objective endpoint is the proportion of tibial neuromodulation subjects considered a UUI responder at 6 months after device implant. A subject is considered a UUI responder if they meet the UUI responder criteria as defined in the voiding diary analysis section 7.2.2.

**Performance Requirements:** The null hypothesis will be rejected if the one-sided p-value is less than 0.025. Only the two-sided p-value will be reported.

**Rationale for Performance Criteria:** The proposed study design includes a primary objective performance goal of 40%. The performance goal defines an active historical control for this study and was defined to position the TNM outcome between the expected performance for medications and the more complex SNM treatment.

**Sample Size Justification:** The sample size justification for the primary objective is provided in section 6.

**Analysis Methods:** The analysis for UUI responder rate will be summarized at 6 months after implant. If 5% of the data or fewer are missing for the primary analysis, no imputation will be used, and the objective will be tested using a binomial test for the Complete Case analysis set. Otherwise, missing data will be imputed for the Full Analysis Set as specified in section 7.4, and the objective will be tested using a Z-test. The two-sided 95% confidence interval will also be provided.

**Determination of Subjects/Data for Analysis:** The primary objective analysis will include all subjects from the Full Analysis Set (i.e., all implant attempted subjects) as defined in section 7.1.3.

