**Supportive and Sensitivity Analyses:** There are no requirements or expectations for the results of the supporting and sensitivity analyses. They are meant to investigate the robustness of the study results and/or to provide further details on the therapy effects.

Additional supporting analyses to further understand the primary objective will be completed through analyses of the change in UUI (secondary objective) and percentage change in UUI (additional measure).

To assess the robustness of the primary objective results under the influence of missing data, sensitivity and subgroup analyses will be conducted using alternative missing data methods and by including different subsets of subjects. The first sensitivity analysis will be completed including subjects from the Primary Objective Complete Case analysis set. This analysis set will be used for a second sensitivity analysis which will be completed including only subjects who received stimulation ('As treated analysis') at the 6-month follow-up visit. An analysis will also be completed to evaluate UUI responder rate differences between different stimulation programs, comparing stimulation programs only if there are an adequate number of subjects in each stimulation program to ensure a stable estimate of response. A tipping point sensitivity analysis will also be completed. A final sensitivity analysis will be conducted on the Primary Objective Complete Case analysis set assigning response failure for the following subjects: those who took any dose of OAB medication in the 2 weeks prior to the diary collection period, and those who received an advanced therapy at any time from implant to the 6-month follow-up visit.

Complete Case analysis set subgroup analyses will be done for the following subject groups: sex, age (divided by median age; divided by age 65), race, and ethnicity. Subjects on the demographic cut point will be added to the adjacent group containing fewer subjects. Any subgroup with less than 10 subjects will not be reported.

As an exploratory analysis to assess if treatment effect differs by study center, a supporting analysis will be completed, as described in 7.3. This analysis will test whether the treatment effect is homogeneous between study centers for the UUI responder rate at 6 months.

UUI responder rate will be assessed over time through 24 months as part of the additional measures.

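### Protocol and SAP give different medication windows for the 6-month sensitivity analysis on added OAB treatment, and neither covers every diary day

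*SAP*

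**What the plan says.** The final sensitivity analysis in SAP 7.9.1.1, run on the Primary Objective Complete Case set, scores two groups as non-responders. The medication group is "those who took any dose of OAB medication in the 2 weeks prior to the diary collection period". For the other group the SAP sets a much longer window: "those who received an advanced therapy at any time from implant to the 6-month follow-up visit". Protocol 14.4.1 describes the same analysis with one window for both treatments: "assigning response failure for all subjects who took OAB medication or received an advanced therapy from implant to the 6-month follow-up visit".

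The main responder definition (Protocol 14.1.5, SAP 7.2.2) has no rule for added treatment. It compares daily episode rates, and "All diaries which are greater than 48 hours will be used for analysis".

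Protocol 10.1 has the 6-month diary start about a week before the visit, with an exception: "If the diary is not able to be completed prior to the visit, it will be completed immediately following the study visit". SAP 7.2.2 likewise accepts diaries kept after the visit.

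Under Protocol 10.1 and 10.5, adding OAB treatment before the 12-month visit is a deviation. A voiding diary showing less than 50% improvement is required before any such treatment starts. Medication goes on a dedicated log; new advanced therapies are recorded at follow-up visits (Protocol 10.5).

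**The concern.** The trial has a single arm, so a subject who improves on an added drug or therapy and records that improvement in the 6-month diary counts as a response to tibial neuromodulation. In the visible text, this sensitivity analysis is the one 6-month responder analysis that removes such subjects from the responders. The As Treated set (SAP 7.1.3) is defined by stimulation received. The long-term analysis that follows SAP 7.9.2.4 excludes subjects with added treatment instead of scoring them as failures.

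Two things look wrong. The documents disagree on which medication use counts, so the reported result depends on which one the analyst follows. Also, the windows do not fully cover the days on which the endpoint is measured. At stake is whether the check does what it is meant to do, not whether the primary test is valid.

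**Working it through.** **The plan's own figure.** Inputs from SAP 6: n = 121, null rate 0.40, alternative 0.55, one-sided alpha 0.025. With the exact binomial, the smallest r with P(X ≥ r | 0.40) ≤ 0.025 is r = 60, where P(X ≥ 60 | 0.40) = 0.0204. Power is P(X ≥ 60 | 0.55) = 0.9009, which agrees with the stated figure of at least 90%. None of this depends on the sensitivity windows.

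**Window lengths.** Inputs: implant is day 0 and the 6-month visit is targeted at day 180, allowed from 150 to 210 (Protocol Table 5). The diary starts about 7 days before the visit and lasts 3 days (Protocol 10.1).

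- Diary: 180 − 7 = day 173, so days 173–175.
- SAP medication window: 173 − 14 = day 159, so days 159–172, which is 14 days.
- Protocol medication window: days 0–180.
- Ratio: 14/180 = 7.8%. For a visit on day 150 it is 14/150 = 9.3%; on day 210, 14/210 = 6.7%.
- Diary completed after the visit: about days 180–183. The literal SAP medication window is then days 166–179, and the visit-based windows close at day 180.

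**What each text counts as failure.**

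| Added treatment | Protocol 14.4.1 | SAP 7.9.1.1, literal |
|---|---|---|
| *Diary before the visit (days 173–175)* | | |
| Medication on days 0–158 only | Failure | Not counted |
| Medication on any of days 159–172 | Failure | Failure |
| Medication on diary days only | Failure | Not counted |
| Advanced therapy up to day 180 | Failure | Failure |
| *Diary after the visit (about days 180–183)* | | |
| Medication first taken after the visit, by the last diary day | Not counted | Not counted |
| Advanced therapy first given after the visit, by the last diary day | Not counted | Not counted |

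Medication carried on from the prior 2 weeks into the diary is already caught by both texts. The uncovered stretch is about 3 diary days in either case.

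**How far the choice of window could move the estimate (illustration).** With 121 complete cases, each responder rescored as a failure lowers the rate by 1/121 = 0.83 percentage points. At the planned 55%, about 67 of 121 respond. Rescoring 8 of them (8/121 = 6.6% of subjects) leaves 59, one below the primary test's count of 60. Let f be the share of all subjects who are diary responders and whose medication use falls inside the protocol window but outside the SAP window. The documents give no value for f, so it is assumed. P(X ≥ 60 | 0.55 − f) is 0.901 at f = 0, 0.857 at 1%, 0.801 at 2%, 0.733 at 3% and 0.572 at 5%. The count of 60 is only a yardstick here, because the sensitivity analysis has no threshold. These figures compare the two documents' medication windows; they do not measure the few-day gaps.

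**The case against.** The strongest reply is that this analysis decides nothing. SAP 7.9.1.1 attaches no required result to it. A reader might infer that the gaps raise the chance of a false success. They do not: the primary test flags nobody for added treatment, and its error rate is the same whichever window the sensitivity analysis uses. That part of the reply stands in full.

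Second, falling into a diary-day or post-visit gap is hard. The subject must breach the 12-month restriction and start treatment within a few days. If no earlier diary has confirmed non-response, that is a second deviation. Deviations are summarised by type (SAP 7.1.2). This stands, and is why the gaps are called small. It does not make the check redundant. A subject who followed the confirming-diary rule is a documented non-responder, and a later response on added treatment is what this analysis exists to catch.

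Third, the 2-week lookback matches the baseline washout and may be deliberate. That is accepted; the lookback is not criticised. A reader might go further and argue that baseline diary days are protected while 6-month diary days are not, since eligibility requires "No OAB pharmacotherapy for 2 weeks prior to completion of the baseline voiding diary". The contrast is weak. The synopsis says "Subjects are prohibited from additional OAB treatment until after the 12-month follow-up visit, starting two weeks prior to the baseline voiding diary", and that restriction covers the 6-month diary days as well. Protocol 10.1 and 10.5 also anchor the washout at the start of the diary.

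Fourth, a reader might object to the Complete Case set, because above 5% missing data the primary test moves to imputation: "Otherwise, missing data will be imputed for the Full Analysis Set as specified in section 7.4". Both documents specify complete cases for this check, and any observed 6-month response that added treatment could affect belongs to a subject in that set. A repeat on the Full Analysis Set is therefore optional.

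**Conclusion.** The point holds in limited form. The two documents define the same sensitivity analysis with different medication windows, about 14 days against about 180 at the target visit. The literal SAP medication window omits the diary days. The visit-based windows, which are advanced therapy in the SAP and both treatments in the protocol, can close up to about 3 days before a post-visit diary ends. The advanced-therapy window itself is the same in both documents.

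The effect of the few-day gaps is probably small. The effect of choosing one medication window over the other depends on how many responders used medication earlier in follow-up, which the documents do not say.

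The documents do not support calling the change unexplained or undisclosed. SAP 7.12 (Changes to Planned Analysis) is listed in the contents but is not in the text available for review, so whether it gives the reason is not judged. The statement that no other 6-month responder analysis handles added treatment is likewise limited to visible text, since parts of the additional-measures section are redacted. The day counts assume a visit on target and a diary started 7 days earlier.

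**What to change.** Replace the rule in the final sensitivity analysis of SAP 7.9.1.1 with text to this effect:

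> Subjects are scored as non-responders if they (a) took at least one dose of OAB medication between 2 weeks before the first day and the last day of the 6-month diary, inclusive, or (b) received an advanced therapy between implant and the later of the 6-month visit and the last day of that diary. A second version scores as non-responders all subjects with either treatment between implant and that same end point.

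The second version is the Protocol 14.4.1 analysis, with its end moved only when the diary runs past the visit. Taking the later date keeps both windows from ending earlier than now planned when the diary precedes the visit. The SAP should also state that its medication window differs from Protocol 14.4.1 and give the reason, so that the two are reconciled.

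Medication dates come from the existing log. Where a diary was completed after the visit, a data query should confirm whether an advanced therapy was added by its last day. New advanced therapies are recorded at follow-up visits, and the pre-market analysis starts once all 6-month visits are complete (SAP 7.8).

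The cost is a SAP revision, one extra analysis version, a short query for a subset of subjects, and a sensitivity estimate that may come out lower. The primary endpoint, alpha, power, sample size and treatment rules do not change.

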## 7.9.2 Secondary Objective(s)

The following secondary objectives have specific hypotheses to be tested. After the primary objective is met, these four secondary objectives will be tested as described in 7.5.

### 7.9.2.1 Secondary Objective – UUI Change

To demonstrate an improvement from baseline to 6 months in number of UUI episodes in subjects with UUI at baseline

**Hypothesis:** The change from baseline in UUI episodes is not 0.

$$H_0: \mu = 0$$

$H_A: \mu \neq 0$

Where  $\mu$  = the change in UUI episodes

**Endpoint Definition and Derivation:** A 3-day urinary voiding diary will be used to collect bladder symptoms, including UUI episodes. Calculation of change in UUI is defined in the voiding diary analysis section 7.2.2. A negative change in UUI episodes represents an improvement.

**Performance Requirements:** The null hypothesis will be rejected if the two-sided p-value is determined to be significant, as described in section 7.5.

**Sample Size Justification:** Data from published studies or studies presented at conferences on TNM outcomes at 3, 6, and 9 months were used as starting points to estimate expected reduction in UUI episodes as well as expected patient-to-patient variability. Assumption on the expected mean difference (-2.0 episodes per day) and standard deviation (3.5 episodes per day) was used to assess statistical power. Presuming a two-sided, one-sample t-test with alphas ranging from 0.013 to 0.05, power is calculated to be no less than 99% for any of the scenarios examined with a sample size of 121 subjects. Additionally, the minimum detectable change in mean episodes was calculated to be as low as -1.0.

**Analysis Methods:** The analysis for change in UUI will be summarized for baseline, at 6 months after implant, and for the change from baseline. If 5% of the data or fewer are missing for the analysis, no imputation will be used, and the objective will be tested using a paired t-test following the multiple testing strategy described in section 7.5. If more than 5% of the data are missing, missing data will be imputed as specified in section 7.4. If non-normality of the data is detected via a significant ( $p<0.05$ ) Shapiro-Wilk test, a Wilcoxon signed-rank test will replace the t-test.

**Determination of Subjects/Data for Analysis:** The change in UUI analysis will include all subjects from the Full Analysis Set (i.e., all implant attempted subjects) as defined in section 7.1.3.

**Supportive and Sensitivity Analyses:** There are no requirements or expectations for the results of the supporting and sensitivity analyses.

Additional supporting analyses to further understand the UUI secondary objective will be completed through analyses of the percentage change in UUI (additional measure).

To assess the robustness of the objective results under the influence of missing data, sensitivity analyses will be conducted using alternative missing data methods. The first sensitivity analysis will be completed including subjects from the Secondary Objective (UUI Change) Complete Case analysis set. This analysis set will be used for a second sensitivity analysis which will be completed including only subjects who received stimulation ('As treated analysis') at the 6-month follow-up visit. A final complete case sensitivity analysis will be performed comparing the change in UUI episodes to a performance goal of 1 episode/day.

UII change from baseline will be assessed over time through 24-months as part of the additional measures.

